PROTOCOL

**“Clinical Evaluation of an Experimental Urethane Dimethacrylate
Resin Based Composite”**

NCT0201882

Purpose: This double blind randomized, controlled prospective clinical trial will compare the clinical success of two tooth colored resin composite dental filling materials- TPH3 (Dentsply Caulk) and an experimental urethane dimethacrylate resin based composite resin (Dentsply Caulk) for wear resistance, staining and marginal seal using modified Ryge criteria to evaluate the posterior restorations for 24 months in duration.

Study Objectives

The purposes of this clinical trial is to evaluate two composite resins used to restore Class I and Class II cavities in teeth of adults. The clinical study will evaluate the resin composite restorations placed in Class I and Class II cavity preparations for anatomic form, color match, marginal integrity, marginal discoloration, proximal contact, polishability, caries, sensitivity, gingival index, staining, wear, and thermal response for 24 months..

Study Design

The study will be double blind randomized, controlled clinical evaluation of similar sized class I and class II with both dental restorative materials placed in a single patient. Both esthetic restorative materials will be bonded with a single bonding agent Prime and Bond Elect (Dentsply Caulk).

Randomization: teeth that require restorations and satisfy the inclusion criteria parameters will be randomly selected. Code R will be assigned to the most anterior tooth or located on the right. Code T will be assigned to the most posterior tooth or located on left. See randomization scheduled (appendix 3). Sponsor will blind both esthetic bonding materials and label them code R and code T.

The study will be conducted in the Division of General Dentistry at Eastman Institute for Oral Health University of Rochester. The study will evaluate the pair of composite resin restorations over a two year period.

50 adult patients aged 18 - 85 yearsold will be recruited into the study. Based on previous clinical trials, the average attrition rate for a two year clinical trial is approximately 10% per year. To assure that 30 restorations per material are available at the three year recall, 100 restorations (50 of each material) will be placed assuming a 20% attrition rate.

Investigators

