Two light-cured resin composites: (TPH 3, Dentsply Caulk and an Experimental urethane dimethacrylate resin based composite resin, Dentsply Caulk) will be used to restore teeth with moderate-large size class I or class II cavity preparations. Each composite resin will be used with Prime and Bond Elect bonding agent. All restored teeth will be in occlusion with at least one proximal contact for each class II restorations with an adjacent tooth. Cavity preparations will be prepared for all restorations following rubber dam isolation unless it is not possible due to abnormal anatomic considerations.

Cavity preparation design. To be included in this study restorations must have a buccal to lingual isthmus width equal to or greater than 1/3 the distance from buccal to lingual/palatal cusp tips, 75% of the restorations must be Class II.

All prepared margins will be placed ninety degrees to the external tooth surface. Any tooth with a carious or mechanical pulpal exposure will be excluded from the study. Any cavity preparation judged to be within 1mm of pulpal tissue either clinically or radiographically will be lined with Dycal (Dentsply Caulk, Milford, DE) a calcium hydroxide containing liner. Palodent Plus (Dentsply Caulk) or other sectional matrix will be used with class 2 restorations; however a Toffelmire matrix may be used with large preparations. The composite will be photoinitiated with a curing light (Smart Lite, Dentsply Caulk) with an output of at least 750 mW/cm². Output will be recorded for each restoration placed. The resin composite will be placed using an incremental filling technique, beginning with an initial increment in the gingival floor. Subsequent increments will be placed to fill the box. No increment will exceed 2mm.

Investigators will insert 100 restorations. Carbide finishing burs (Midwest 7402, OS 1, OS 2) will be used to remove gross excess, followed by finishing strips and disks (Sof-Lex, 3M, St Paul, MN), and the Enhance system (Dentsply Caulk, Milford, DE). All polishing will be done at slow speed with water spray. After removing the rubber dam the occlusion will be adjusted. Each restoration will be evaluated directly and indirectly at . The direct clinical evaluations will be made using the checklist in table one, a modification of the United States Public Health Services (USPHS) guidelines.

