Each restoration will be evaluated for anatomic form, color match, marginal integrity, marginal discoloration, proximal contact, polishability, caries, sensitivity, gingival index. Indirect wear measurements will be made on casts from impressions made at each recall and baseline.

Two of the trained evaluators (Drs [name], [name], [name] and [name]) who have not placed restorations, will perform post-restorative evaluation at baseline, 6 months, 12

months and 24 months. A consensus will be reached if both evaluators disagree on the restorations' direct assessment. [name] will provide retraining any time throughout the study upon evaluator's request.

Study Visits

Subjects will be evaluated at the Eastman Institute for Oral Health General Dentistry Department. Study visits at 6, 12 and 24 months may be combined with routine dental care visits.

Screening:

Subjects will be screened for study eligibility. Two bitewing radiographs will be taken of teeth in need of restorations.

If a subject is eligible, the informed consent process will initiate. Subject will be given a consent form by a member of the study team and discuss study procedures. Subjects will be informed about the option of taking the consent form home and schedule an appointment at their convenience as well as that their participation is strictly voluntary and participation will not affect their care.

If the subject wishes to participate in the study a copy of the consent form will be given and pre-operative assessments indicated on schedule of events (appendix 1) will be administered. If the subject satisfies inclusion criteria for the study and wishes to receive the restoration at this visit, the study coordinator will assign products code according to subject number listed on the randomization list (appendix 3) and restorations will be placed by one of the sub-investigators. Subject can choose to schedule a separate appointment for restorations placement and no additional study procedure will be required at the restorative visit.

Baseline (one week after the restorations)

Study procedure:

Subject's restorations will be evaluated by two investigators other than the investigator who placed the restorations for the following:

- anatomic form,
- color match,
- marginal integrity,
- marginal discoloration,
- proximal contact,
- polishability
- caries.
- sensitivity
- Gingival index – (a dental probe will gently stimulate gingival tissues around the two restored teeth).

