C =	There is visual evidence of marginal discoloration at the junction of the tooth structure and the restoration that has penetrated along the restoration in a pulpal direction.

Proximal Contacts	
A =	Tight proximal contacts evaluated with dental floss.
B =	Proximal contacts are weak but present.
C =	No proximal contacts but not visibly open.
D =	Visibly open contacts.

Polishability	
Alpha=	Smooth & highly shiny, similar to enamel
Bravo 1=	Smooth & satin, highly reflective
Bravo 2=	Smooth & shiny but not highly reflective
Charlie=	Rough & shiny, satin, somewhat reflective
Delta=	Rough & dull or satin, not reflective
Eta=	Unacceptable polish

Caries	
A =	Absent
B =	Present

Gingival Index	
0 =	Normal gingival.
1 =	Mild inflammation, slight change in color, slight edema, no bleeding on probing.
2 =	Moderate inflammation, redness; edema and glazing; bleeding on palpation.
3 =	Severe inflammation, marked redness and edema, ulceration, tendency to spontaneous bleeding.

Appendix 3

Randomized list

Subject

#	Code R	Code T
1	T	R
2	R	T
3	R	T
4	R	T
5	T	R
6	T	R
7	R	T
8	R	T
9	R	T
10	R	T
11	R	T
12	T	R
13	T	R
14	T	R
15	T	R
16	T	R
17	T	R
18	R	T
19	R	T
20	R	T
21	R	T
22	T	R
23	T	R
24	R	T
25	R	T
26	T	R
27	R	T
28	T	R
29	T	R
30	R	T
31	T	R
32	R	T
33	R	T
34	T	R
35	R	T

Place code **R** on most anterior tooth or on the **left** side of the mouth

Place code **T** on most posterior or on the **Right** side of the mouth

36	T	R
37	R	T
38	T	R
39	R	T
40	T	R
41	R	T
42	R	T
43	T	R
44	R	T
45	R	T
46	R	T
47	T	R
48	T	R
49	T	R
50	T	R

PROTOCOL Addendum

**“Clinical Evaluation of an Experimental Urethane Dimethacrylate
Resin Based Composite”**

Purpose: This addendum protocol is a controlled prospective clinical trial to evaluate and compare the clinical success of an additional investigational tooth colored resin composite dental filling material, EsthetX HD (Dentsply/Caulk), to TPH3 (Dentsply Caulk) and to an experimental urethane dimethacrylate resin based composite resin (Dentsply Caulk). Comparison of EsthetX HD (Dentsply/Caulk) to the resin composite materials used in the original protocol is necessary in order to evaluate its clinical performance. Using the modified Ryge criteria, EsthetX HD (Dentsply/Caulk) restorations will be evaluated for wear resistance, staining and marginal seal during a 24 month period.

Study Objectives

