The purpose of this clinical trial is to evaluate and compare an additional composite resin material used to restore Class I and Class II cavities in teeth of adults. The clinical study will evaluate the resin composite restorations placed in Class I and Class II cavity preparations for anatomic form, color match, marginal integrity, marginal discoloration, proximal contact, polishability, caries, sensitivity, gingival index, staining, wear, and thermal response for a 24 months period.

Study Design

The study will be a controlled clinical evaluation of similar sized class I and class II with dental restorative materials placed in a single patient. The esthetic restorative materials will be bonded with a single bonding agent Prime and Bond Elect (Dentsply Caulk).

The study will be conducted in the Division of General Dentistry at Eastman Institute for Oral Health University of Rochester. The study will evaluate the composite resin restorations over a two year period.

Fifty adult patients aged 18 - 85 years old will be recruited into the study. Based on previous clinical trials, the average attrition rate for a two year clinical trial is approximately 10% per year. To assure that 30 restorations per material are available at the two year recall, 50 restorations will be placed assuming a 20% attrition rate.

Investigators

[name] is the Principal Investigator. Drs [name] will conduct the screening examinations and [name] and members of the study team will obtain consent.. Experienced sub-investigators will place the tooth colored restorations.. Two of the study team investigators who have not placed the restorations will complete the baseline, 6 month, 12 months and 24 months recall examinations of the restorations. Investigators will not evaluate the restorations they placed. Baseline evaluations will be conducted one week after the restorations are placed.

Material:

Experimental Material: EsthetX HD improvement composite made by Calk using three lots of the glass filler, which were silanated in a production Resodyn unit at Calk. The raw material, unsilanated glass (also called TPM filler) was provided by TPM company in a production scale. The TPM filler was designed to reduce the stickiness of current EsthetX HD composite.

Duration of the investigation: 24 months

Number of restorations:

50 restorations will be placed to ensure a minimum 30 restorations

Class of restorations:

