Restorations will be placed in separate preparations in Class I and Class II in upper and lower jaw in bicuspid and molars. All teeth will have natural teeth or crowns of bridgework as antagonists. For the clinical evaluation of the resin, specific criteria (table 1 and 2) will be used to evaluate the restorations directly and indirectly.

Distribution of restorations:

EsthetX HD material will be placed on patients who need at least one tooth restored, with a maximum of two restorations per each patient. A maximum of 25% of the restorations will be class I the remainder will be class II restorations.

Size of cavities:

Moderate-large cavities with an isthmus width greater than or equal to 1/3 the intercuspal distance (1/3 the distance between the cusp tips) will be selected for this study.

Subject Population:

Enrollment for subjects who received composite restoration TPH3 Spectra HV (Dentsply Caulk) and an experimental urethane dimethacrylate resin based composite resin (Dentsply Caulk) is complete and currently on the follow-up phase. An additional 50 subjects for this investigation will be selected from patients of the University of Rochester at Eastman Institute for Oral Health. Fifty subjects who are generally seeking routine dental care and need one or two restorations on asymptomatic posterior teeth and aged 18-85 will be recruited.

Inclusion Criteria:

- must have given written consent to participate in the trial
- must be in need of at least one restorations in natural tooth
- replacement restorations with or without caries are acceptable
- must be available for the required post-operative follow-up visits
- restorations to be in bicuspid, 1st or 2nd molars
- restorations to be in contact with opposing natural or crowned teeth
- class II restorations must have at least one proximal contact

- restorations must have a buccal to lingual/palatal width equal to or greater than 1/3 the distance from buccal to lingual/palatal cusp tips
- 75% of the restorations must be Class II
- all restorations must have at least one occlusal contact in habitual closure

Subjects may be excluded for this study if they:

- have severe medical complications (organ transplants, long term antibiotic or steroid treatment, cancer or immunocompromised) or disabilities who may not be able to tolerate the time required to complete the restorations or to provide adequate oral hygiene

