Investigators will insert 150 restorations. Carbide finishing burs (Midwest 7402, OS 1, OS 2) will be used to remove gross excess, followed by finishing strips and disks (Sof-Lex, 3M, St Paul, MN), and the Enhance system (Dentsply Caulk, Milford, DE). All polishing will be done at slow speed with water spray. After removing the rubber dam the occlusion will be adjusted. Each restoration will be evaluated directly and indirectly at The direct clinical evaluations will be made using the checklist in table one, a modification of the United States Public Health Services (USPHS) guidelines.

Each restoration will be evaluated for anatomic form, color match, marginal integrity, marginal discoloration, proximal contact, polishability, caries, sensitivity, gingival index. Indirect wear measurements will be made on casts from impressions made at baseline, 12 and 24 month recall visit

Two of the trained and calibrated evaluators (Drs [name], [name], [name], [name] and [name]) who have not placed restorations, will perform post-restorative evaluation at baseline, 6 months, 12 months and 24 months. A consensus will be reached if both evaluators disagree on the restorations' direct assessment. [name] will provide retraining any time throughout the study upon evaluator's request.

Study Visits

Subjects will be evaluated at the Eastman Institute for Oral Health General Dentistry Department. Study visits at one week, 6, 12 and 24 months may be combined with routine dental care visits.

Screening:

Subjects will be screened for study eligibility. Two bitewing radiographs will be taken of teeth in need of restorations.

If a subject is eligible, the informed consent process will initiate. Subject will be given a consent form by a member of the study team and discuss study procedures. Subjects will be informed about the option of taking the consent form home and schedule an appointment at their convenience as well as that their participation is strictly voluntary and participation will not affect their care.

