If the subject wishes to participate in the study a copy of the consent form will be given and pre-operative assessments indicated on schedule of events (appendix 1) will be administered. If the subject satisfies inclusion criteria for the study and wishes to receive the restoration at this visit a restoration or two restorations will be placed by one of the sub-investigators. Subjects can choose to schedule a separate appointment for restorations placement and no additional study procedure will be required at the restorative visit.

Baseline (one week after the restorations)

Study procedure:

Subject's restorations will be evaluated by two investigators other than the investigator who placed the restorations for the following:

- anatomic form,
- color match,
- marginal integrity,
- marginal discoloration,
- proximal contact,
- polishability
- caries.
- sensitivity
- Gingival index – (a dental probe will gently stimulate gingival tissues around the two restored teeth).
- Impressions for wearing and contact assessments will be taken. – A soft material is placed on the subject's upper or lower dentition or both (depending on the location of restored teeth). As the material hardens will leave a negative print of the subject's dentition. A stone material is then poured into the impression resulting in a cast which will allow restorations' wearing and contact measurements.
- Two radiographs will be taken. These radiographs are taken in addition to the screening radiographs as they will provide a post-restorative baseline.

- Photographs of restoration(s) will be taken with a digital camera. Subjects will be identified according to their assigned subject number.

Standard of care: Patient is scheduled a week after a restoration is placed for follow up. Radiographs may be taken for possible overhang and/or patient's complaints. Patients will be asked to report complaints and possible adverse events.

6 months follow-up

Study procedure:

Subject's restoration (s) will be evaluated by two investigators other than the investigator who placed the restorations for the following:

- anatomic form,
 - color match,
 - marginal integrity,
 - marginal discoloration,
 - proximal contact,
 - polishability
 - caries.
 - Photographs of both restoration
 - Gingival index score will be collected.
-

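### EsthetX HD goes to a separately enrolled cohort with no allocation described, so the addendum cannot support the controlled, same-patient comparison that it announces

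*Combined protocol and SAP*

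**What the plan says.** **Aim.** The addendum's Purpose presents a controlled prospective trial and states: "Comparison of EsthetX HD (Dentsply/Caulk) to the resin composite materials used in the original protocol is necessary in order to evaluate its clinical performance".

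**Design.** The addendum's Study Design reads: "The study will be a controlled clinical evaluation of similar sized class I and class II with dental restorative materials placed in a single patient". By contrast, the original protocol describes itself as double blind and randomized in both its Purpose and its Study Design. The addendum uses neither term in those two sections.

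**Cohorts.** The addendum's Subject Population section says that enrolment to TPH3 and the experimental resin "is complete and currently on the follow-up phase" and that 50 more subjects will be recruited. Its Inclusion Criteria require a need for one restoration or more; the original required two or more.

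**Allocation.** In the original Randomization paragraph, "Sponsor will blind both esthetic bonding materials and label them code R and code T". Under the original Screening heading, "the study coordinator will assign products code according to subject number listed on the randomization list (appendix 3". The matching addendum text says only that "a restoration or two restorations will be placed by one of the sub-investigators". The addendum has no counterpart to Appendix 3. Its Appendix 1 keeps a row that combines subject-number assignment with randomization.

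**Counts.** Original Materials and Methods: "Investigators will insert 100 restorations". Addendum Materials and Methods: "Investigators will insert 150 restorations".

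**Analysis.** The addendum's Data Analysis section reports percentages per category and uses them to describe trends across groups. It then lists fixed limits, among them 10% for score C on color match, marginal discoloration and marginal integrity, and 5% for caries. It does not say that the EsthetX HD contrast is non-randomised.

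**The concern.** The original trial compares two materials within a patient under a randomisation list, so patient factors are balanced by design. The addendum keeps the language of control and of materials sharing a patient, and calls the comparison with the two original materials necessary. If EsthetX HD is given only to other people, enrolled later under a different entry rule, that protection is absent. A gap in raw percentages could then come from patient selection, placement period or technique as easily as from the resin. A reader of the report would take it for a controlled result.

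**Working it through.** **1. The plan's own attrition figure.** The addendum's Study Design places 50 restorations to have 30 at two years with 20% attrition.
- Forward: 50 × (1 − 0.20) = 40 expected.
- Backward: 30 / (1 − 0.20) = 37.5, so 38 would be enough.

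The figure of 50 does not follow from 30 and 20%, but it exceeds the need. There is no shortfall and this point does not depend on it. I use n = 40 below, with n = 30 as the stated minimum.

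**2. Can a patient receive EsthetX HD beside a comparator?** Four places in the addendum bear on this:
- Subject Population: enrolment to the two original materials is closed, and the new subjects are additional.
- Distribution of restorations and Inclusion Criteria: one restoration is enough for entry, with at most two EsthetX HD restorations per patient.
- Number of restorations: 50, with a minimum of 30.
- Screening: one or two restorations are placed, and no product code is drawn.

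None of these provides for a TPH3 or experimental-resin tooth in a new subject. Only the Study Design sentence and the randomization label in Appendix 1 point the other way, and neither comes with a method.

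**3. The figure of 150.** 100 (original) + 50 (addendum) = 150, which fits EsthetX HD alone being added. But 50 patients × 3 materials = 150 as well, so the total does not settle the matter. The addendum's increment rule also still names TPH 3 Spectra HV. The Subject Population text is what carries the conclusion.

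**4. Restorations per subject.** Three statements in the addendum disagree:
- Study Design: 50 restorations in 50 subjects, or 50/50 = 1 each.
- Distribution of restorations: one or two each, so 50 subjects would give between 50 × 1 = 50 and 50 × 2 = 100.
- Data Analysis: 100 restorations in 50 subjects, or 100/50 = 2 each.

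**5. What differs between cohorts and what does not.**
- Different: the enrolment period, the number of restorations needed for entry, the liner named for preparations within 1 mm of the pulp, and the curing light named (same 750 mW/cm² minimum).
- Unchanged: site, bonding agent, cavity-width rule, Class I/II limits, scoring criteria and visit times.

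Recall periods may overlap, because the original subjects are still being followed.

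**6. Precision of EsthetX HD's own rate.** Assumptions: one restoration per patient, and event counts chosen to sit on the limits. Exact (Clopper-Pearson) 95% interval for x events in n: lower = 2.5% quantile of Beta(x, n − x + 1); upper = 97.5% quantile of Beta(x + 1, n − x).

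| x/n | Rate | Exact 95% interval |
|---|---|---|
| 2/40 | 5.0% | 0.6% to 16.9% |
| 4/40 | 10.0% | 2.8% to 23.7% |
| 0/40 | 0% | 0% to 8.8% |
| 0/30 | 0% | 0% to 11.6% |

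These intervals describe sampling error only.

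**The case against.** The addendum is partly open about its design. It leaves out the double-blind and randomized labels, omits the code assignment, and says that the earlier enrolment has closed. A trial can be called controlled with a comparator that is neither randomised nor concurrent. The Study Design sentence no longer says that both materials go into one patient, as the original did, and might loosely mean up to two EsthetX HD restorations per person. The analysis is descriptive, no between-material test is planned, and the numerical limits need no comparator.

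Much of this stands. It means that no test fails and that EsthetX HD can be judged on its own rates. It does not rescue the comparison. The Purpose rests the evaluation on that comparison, the Study Design still speaks of materials in the plural within one patient, and no sentence tells the reader that the contrast is between separately enrolled cohorts.

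A reader might go further and infer that the addendum is open-label, since everyone in the new cohort has the same material. The documents do not support that. Evaluators do not score restorations they placed, the materials are said to share color, consistency and odor, and nothing says whether evaluators know the cohort. The supportable statement is that masking is not described.

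**Conclusion.** The concern holds. As planned, a difference in raw percentages between EsthetX HD and TPH3 or the experimental resin mixes material with cohort and cannot be attributed to the material. The fixed limits remain usable for EsthetX HD alone. This rests on the Subject Population text and on the absence of any described allocation.

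The size of the cohort bias is unknown, because the documents give no figure for it. The intervals above show how imprecise one cohort's own rates would be, under assumed counts and one restoration per patient. They are not a measure of the bias.

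Two other inferences go too far. The total of 150 is consistent with no new control restorations but does not prove it. The liner and curing-light differences are differences between cohorts, but the documents do not show that either affects outcome.

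**What to change.** 1. State that the EsthetX HD conclusion rests on its own rates, with exact 95% intervals, against the Data Analysis limits at one named scheduled visit. The limits are written for 18 months, and the visits are at baseline, 6, 12 and 24 months. Allow for clustering if any patient contributes two restorations.
2. State that any contrast with TPH3 or the experimental resin is non-randomised, separately enrolled and exploratory. Show it as a difference with a 95% interval, beside a table by cohort of tooth type, Class I/II, arch and restorations per patient.
3. Delete the single-patient phrase from the addendum's Study Design and the word randomization from the Appendix 1 row, keeping subject-number assignment.
4. Reconcile the restoration counts in the addendum's Study Design, Distribution of restorations and Data Analysis sections, and the TPH 3 Spectra HV mention with the closed enrolment. Reconcile the liner and curing-light passages, or declare them as cohort differences.
5. State whether evaluators are masked to material and to cohort.

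The cost is wording, intervals and one descriptive table, with no new data. The downside is a weaker comparative claim for EsthetX HD.
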